4.5.2 Economic burden and time away

The cost of one Activa IM-Nail™ (approximately \$400) is about four times higher than that of a traditional titanium elastic nail (TEN; approximately \$100). However, the cost of implant removal is approximately \$1,900 [6,37], and the additional implant cost may therefore be offset. In a cost analysis that included both direct medical costs and indirect costs related to lost work time, the average cost saved per patient by using absorbable implants ranged from \$410 to \$903 [37].

Removal surgery is not only a socioeconomic concern. Parents typically need time off work for outpatient visits related to surgical planning, on the day of surgery, and potentially for days after treatment. This may create financial strain and, in some cases, concerns regarding job security. Similarly, the child will require time away from school.

4.5.3 Operation room burden

Because most implants in children are routinely removed, implant removal procedures consume substantial operating room capacity. Use of bioabsorbable implants may reduce the need for elective removal surgery, thereby freeing capacity for other procedures.

4.6 Current status of research in this area

To assess feasibility and safety, we conducted a prospective preliminary study including 18 children with forearm fractures treated with bioabsorbable intramedullary nails (BIN). No serious adverse events

or serious adverse device effects were observed. All fractures healed, and all children regained normal arm function within 3 months.

An international multicenter study of 76 children treated with the Activa IM-Nail reported few complications. In two cases, a small implant fragment was sheared off by the sharp fracture edge, necessitating secondary surgery for fragment removal. The Activa IM-Nail Technique Guide has subsequently been revised to emphasize additional caution when advancing the nail across the fracture site and to recommend only light hammer blows [38].

In Finland, the Activa IM-Nail has been investigated since 2011 in a randomized controlled trial comparing BIN with TEN. Both short- and long-term follow-up demonstrated similarly good outcomes [7,30].

To date, no studies have evaluated differences in time to bone union when comparing BIN with TEN. Furthermore, time to healing in PDFF has not been rigorously investigated in a prospective setting.

5 Primary and secondary objectives

5.1 Primary objective

- To investigate time to bone healing (weeks) in PDFF treated with bioabsorbable intramedullary nails (BIN) versus titanium elastic intramedullary nails (TEN).

5.2 Secondary objective(s)

- To investigate and describe
 - Functional outcome
 - Pain and discomfort
 - Refracture rate
 - Surgical complications
 - Implant-related complications
 - Patient-reported outcomes
 - Costs related to surgery
- To investigate time to bone healing (weeks) in PDFF treated non-operatively

5.3 Hypothesis

We hypothesize that time to bone healing with BIN is non-inferior to time to bone healing with TEN in the treatment of PDFF.

6 Study design

Given the potential advantages of bioabsorbable intramedullary nails (BIN), it is clinically acceptable for BIN to have a limited delay in healing compared with TEN, provided overall outcomes remain acceptable. Therefore, this study is designed as a non-inferiority trial.

A single-center, randomized, parallel-group, non-inferiority design with blinding of relevant parties has been selected, with stratification by age. The study design will follow CONSORT guidance for reporting non-inferiority trials [39].

6.1 Study population and patient enrollment

The study will be conducted at Copenhagen University Hospital – Herlev and Gentofte, Capital Region of Denmark. The hospital has a catchment area of approximately 600,000 inhabitants, including about 80,000 children aged 3–13 years.

This study investigates the treatment of pediatric forearm fractures and therefore cannot be conducted in consenting adults. Forearm fractures occur across all pediatric age groups, and it is not feasible to restrict inclusion to older children only. The study is expected to have potential direct benefit for participating patients and to generate knowledge that may improve care for future patients with the same condition.

Initial assessment in the emergency department will follow standard of care and will be independent of subsequent treatment allocation. The assessment includes medical history, physical examination, and radiographs in anteroposterior (AP) and mediolateral (ML) projections.

All operations will be performed at Herlev Hospital by orthopedic trauma surgeons.

6.1.1 Inclusion criteria

The inclusion criteria are aligned with the existing literature for the comparator (TEN).

Inclusion criteria

- Children aged 3 to 13 years with open physes
- Acute traumatic pediatric diaphyseal forearm fracture (PDFF) of the radius, ulna, or both
- Fracture characteristics:
 - Complete fracture (not unicortical or greenstick)
 - Displacement >50% of bone width, and/or angulation >10° in any plane
- Written informed consent obtained, including:
 - Ability of the parent(s) to understand the patient information and informed consent form (eICF)
 - Signed and dated ethics committee (EC)-approved eICF

6.1.2 Preoperative exclusion criteria

• Contraindications

- Any condition in which internal fixation is contraindicated (e.g., active or suspected infection)
- Grossly open fractures (Gustilo–Anderson grade > II)

• Exclusion criteria

- Fracture occurred more than 2 weeks prior
- Previous ipsilateral forearm fracture (risk of an obliterated/closed medullary canal)
- Fractures not suitable for intramedullary nailing (e.g., multifragmentary, metaphyseal, or epiphyseal fractures)
- Concurrent ipsilateral wrist or elbow involvement (e.g., Monteggia or Galeazzi variants)
- Inability to participate in follow-up (e.g., no Danish CPR number/contact information, plans to move away within 3 months, or inability to attend visits despite offered scheduling flexibility)
- Pre-existing bone pathology (e.g., tumor, osteogenesis imperfecta, or other bone disease affecting bone quality/healing)
- Participation in another medical device or medicinal product study within the previous month that, in the opinion of the Principal Investigator (PI), could influence the results of the present study

6.1.3 Intraoperative exclusion criteria

- Intraoperative findings indicating that only Treatment 1 (BIN) is appropriate
- Intraoperative findings indicating that only Treatment 2 (TEN) is appropriate
- Intraoperative decision to use implants other than the investigational devices (e.g., plate fixation or external fixation)

6.1.4 Enrollment of participants

The study site will identify all eligible patients, defined as those who meet all inclusion criteria and none of the exclusion criteria.

6.1.4.1 Identification/prescreening

Potential participants may present to the Emergency Department (ED), the outpatient clinic (OC), or be referred from local clinics or other hospitals. Identification of eligible patients will occur during direct clinical contact in the ED or OC and/or through the routine daily review of radiographs obtained in the ED and OC or by referral.

6.1.4.2 Minimal screening log

A minimal screening log will be maintained to document the identification and flow of potentially eligible patients and to support transparency in recruitment (e.g., reasons for non-enrollment). The screening log will contain only the minimum necessary information to fulfil this purpose and will be kept separately from the study database.

For each prescreened patient, the log will include:

- a unique screening ID (assigned at prescreening)
- date of prescreening and the clinical point of identification (e.g., ED / outpatient review)
- eligibility status (eligible / not eligible / pending)
- primary reason for non-enrollment (e.g., not meeting inclusion/exclusion criteria, declined participation, logistical reasons)
- whether informed consent was obtained (yes/no) and, if yes, date of consent

The screening log will not include study outcomes or detailed clinical research data. To prevent duplicate entries and enable follow-up of pending cases, linkage to the medical record is required; this will be limited to a single linkage element (CPR number) and stored in an access-restricted manner. Access to the screening log will be limited to authorized study personnel (PI and delegated research staff) and it will be stored in a secure system (REDCap) with appropriate technical and organizational safeguards.

No study-specific data extraction beyond the minimal screening variables will occur prior to informed consent. Screening log data will be retained in accordance with applicable regulatory and institutional requirements and will be deleted or anonymized when no longer required.

6.1.4.3 Assessment of eligibility

If a patient appears to be a candidate for enrollment, and in accordance with ethics committee (EC) approval, the study team may contact the parents in person (in the ED or OC) to assess interest and confirm the child's eligibility for participation. This initial contact will include a brief prescreening to verify key eligibility criteria and a concise description of the study, and the responsibilities associated with participation.

- Eligible patients/parents will be offered a scheduled study visit as soon as possible.
- Parents will be informed that they may bring an accompanying person (e.g., a support person) to the visit.

6.1.4.4 Study information

If the parents express interest in participation, a member of the research team will conduct the informed consent process face-to-face. The consent discussion will stress that any participation is completely voluntary and will cover the purpose of the study, study procedures, potential risks and benefits, alternatives to participation, and data protection.

- Parents will receive both oral and written information.
- All parents will sign an electronic or written Informed Consent Form (eICF/wICF), as applicable.
- The signed e/wICF will be filed in the Investigator Site File (ISF), and a copy will be provided electronically or written to all signatory.

6.1.4.5 Place of recruitment

Participants will be recruited at Copenhagen University Hospital – Herlev and Gentofte by delegated members of the research team.

6.1.4.6 Informed consent

A more detailed description of the informed consent process is provided in Section 10.

- All participants for whom written informed consent has been obtained will be assigned a unique trial participant number.
- The date of informed consent and recruitment details will be recorded in the study database.
- Participants who commence any study treatment are considered enrolled.
- All enrolled participants will be followed within the study unless participation is terminated prematurely for reasons specified in Section 6.2.17.

6.1.4.7 Recruitment period

The recruitment period is estimated to be 36 months, based on the number of eligible patients managed at our institution over the past 5 years. If recruitment targets are not met by 24 months, the recruitment period will be extended by an additional 12 months.

6.2 Study procedures

The schedule of all follow-up (FU) visits, including imaging procedures, and the data to be collected at each visit are presented in Table 1.

Table 1: Study schedule

Assessment parameters	Pre- intra- and postoperative visits														
				Day 0		Visit X**	Visit 1	Visit 2	Visit 3	Visit Y***	Visit Z***	Visit 9	Visit 10	Visit 11	Visit 12
	Injury	Screening	Pre-treatment visit	Intraoperative	Post-operative / reduction	1 week	2 weeks	4 weeks	6 weeks	8 weeks	10 weeks	12 weeks	6 months	1 year	2 years
Screening/invitation		X													
Eligibility			X												
Patient information and consent			X												
Demographics			X												
Radiographs	X			X*	X	X	X	X	X	X	X	X	X	X	X
Bone age radiograph												X			
Cast removal for ESIN group							X								
Cast removal for BIN group								X							
Cast removal for non-operative group									X						
Clinical exam	X				X	X	X	X	X	X	X	X	X	X	X
Patient Reported Outcome			X			X	X	X	X	X	X	X	X	X	X
Test of Motor Proficiency												X			

All postoperative visits with the defined time windows are calculated from the day of surgery/randomization or reduction (Day 0).

* Fluoroscopy

** For non-operative group only

*** Visit only completed if all fractures are not healed sufficiently at previous visit.

6.2.1 Injury

On the day of injury, the patient is treated according to standard of care. The diagnosis is established on standard forearm radiographs (anteroposterior and lateral views). An above-elbow splint is applied to stabilize the fracture.

6.2.2 Screening

The screening and inclusion process is described in detail in 6.1.

6.2.3 Preoperative visit

The enrollment and informed consent process is described in Section 6.1.4 and Section 10, as well as in the corresponding SOP.

- All patients prescreened against the inclusion and exclusion criteria will be recorded in the Screening Log described in Section 6.1.4.2.
- Screening and baseline data will be entered into the eCRF.

6.2.4 Intraoperative (day 0)

- Confirmation of the indication for treatment and assessment of any contraindications that may have arisen since the preoperative visit
- Verification of intraoperative exclusion criteria
- Assessment for any adverse events (AEs) since the preoperative visit, including documentation and reporting as applicable
- Treatment as described in Section 6.3
- Randomization as described in Section 6.3.6
- Documentation of surgical details
- Source data verification and entry into the eCRF

6.2.5 Postoperative/discharge

- Postoperative ward rounds
- Discharge according to the treatment protocol described in Section 6.3.8 and related SOP
- Documentation of discharge details
- Source data verification and entry into the eCRF

6.2.6 Visit 1 (2 weeks)

- Assessment for any adverse events (AEs) since the previous visit, including documentation and reporting as applicable
- Radiographs
- Cast removal for the titanium elastic nail (TEN) group, if applicable
- Clinical examination and outcome assessments as described in Section 7
- Source data verification and entry into the eCRF
- Scheduling of the next visit
- Appointment for the next visit

6.2.7 Visit 2 (4 weeks)

- Assessment for any adverse events (AEs) since the previous visit, including documentation and reporting as applicable
- Radiographs

- Cast removal for the bioabsorbable intramedullary nail (BIN) group, if applicable
- Clinical examination and outcome assessments as described in Section 7
- Source data verification and entry into the eCRF
- Scheduling of the next visit
- Appointment for the next visit

6.2.8 Visit 3 (6 weeks)

- Assessment for any adverse events (AEs) since the previous visit, including documentation and reporting as applicable
- Radiographs
- Clinical examination and outcome assessments as described in Section 7
- Source data verification and entry into the eCRF
- Scheduling of the next visit:
 - If bone healing is not sufficient, defined as an mRUS < 11 in any fractured bone, a follow-up visit will be scheduled at 8 weeks postoperatively.
 - If bone healing is sufficient (mRUS ≥ 11 in all fractured bones), the next visit will be scheduled at 3 months postoperatively.

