6.2.9 Visit X (8 weeks)

This visit is only performed if bone healing was not sufficient at Visit 3 (6 weeks), defined as mRUS < 11 in any fractured bone.

- Assessment for any adverse events (AEs) since the previous visit, including documentation and reporting as applicable
- Radiographs
- Clinical examination and outcome assessments as described in Section 7
- Source data verification and entry into the eCRF
- Scheduling of the next visit:
 - If bone healing is not sufficient, defined as mRUS < 11 in any fractured bone, a follow-up visit will be scheduled at 10 weeks postoperatively.
 - If bone healing is sufficient (mRUS ≥ 11 in all fractured bones), the next visit will be scheduled at 3 months postoperatively.

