6.2.10 Visit Y (10 weeks)

This visit is only performed if bone healing was not sufficient at Visit X (8 weeks), defined as mRUS < 11 in any fractured bone.

- Assessment for any adverse events (AEs) since the previous visit, including documentation and reporting as applicable
- Radiographs
- Clinical examination and outcome assessments as described in Section 7
- Source data verification and entry into the eCRF
- Scheduling of the next visit

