6.3.7.1 Blinded postoperative documentation

To maintain blinding of participants, parents, and routine postoperative caregivers, a standardized “blinded” postoperative documentation pathway will be used in the electronic health record (EHR). The purpose is to prevent inadvertent disclosure of treatment allocation through operative notes, discharge documentation, or follow-up scheduling, while ensuring that complete and legally compliant source documentation is retained and remains available to authorized clinical staff when needed.

Immediately after surgery, documentation will be split into:

- Blinded postoperative note (visible to routine postoperative care and to families via patient-facing portals, where applicable): A standardized template will be used stating that the participant “underwent intramedullary fixation with one of the two study nails according to randomization,” without naming implant type. The note will include study information (including emergency contact information), non-allocating clinical essentials (diagnosis, reduction status, approach, complications, cast applied, neurovascular status, activity restrictions, analgesia plan, and safety advice).
- Additional operative record (restricted access): An additional operative record containing the implant type, sizes, lot/batch identifiers, and any implant-specific technical details will be completed and

retained as source documentation with access restricted to authorized staff (e.g., operating surgeon, delegated unblinded study personnel, and clinicians requiring access for safety). Implant traceability information (REF/LOT, sizes) will also be recorded in the device accountability log/eCRF as prespecified.

6.3.7.2 *Maintaining blinding despite imaging and clinical routines*

For research outcome assessment, postoperative radiographs will be exported as de-identified copies and edited to conceal implant-specific radiopaque features as described in Section 7.1. Clinical care will continue to rely on unedited radiographs in the medical record. Study staff involved in follow-up assessments will avoid disclosure of allocation, and participants and parents will be asked not to seek information on implant type until after the 6-month visit.

6.3.7.3 *Emergency unblinding*

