7.1.1.4 Blinding of radiographs via standardized image masking

Bioabsorbable intramedullary nails are largely radiolucent, with only a radiopaque tricalcium phosphate tip, whereas titanium nails are inherently radiopaque. To ensure blinded radiographic outcome assessment across treatment groups, all postoperative radiographs will be de-identified and digitally masked prior to review. Using image-editing software, visible radiopaque implant components will be concealed, while preserving full visibility of the fracture region, cortical outlines, and callus formation (Figure 3). All patient identifiers and acquisition metadata will be removed, and images will be assigned a study-specific ID and a non-revealing time point label only.

Image manipulation will be performed by a member of the research team who is not involved in postoperative clinical assessment, outcome evaluation, or statistical analysis, and who will have no role in adjudication of radiographic endpoints. Masking procedures will be documented to ensure consistency. All manipulated images are stored outside PACS. All original unaltered radiographs are stored in the hospital's PACS.

Original follow-up radiograph

Edited radiograph with implant concealed

Figure 3 – Example of original and edited radiograph to blind the assessor to the implant.

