7.1.1.5 Independent review, adjudication, and reliability (quality assurance)

All masked radiographs will be assessed independently by two blinded reviewers (musculoskeletal radiologist and orthopedic surgeon) using a pre-specified scoring manual. Reviewers will undergo a brief calibration exercise prior to study readings. Images will be presented in random order and without access to clinical data or treatment allocation.

Inter-rater reliability for mRUS will be quantified using appropriate agreement statistics (e.g., ICC for total mRUS and weighted kappa for ordinal cortex scores), and intra-rater reliability will be assessed by repeat scoring of a randomly selected subset of examinations after a washout period (e.g., 2–4 weeks), with re-randomization of the re-read set. Discrepant assessments of healing status relevant to the primary endpoint will be resolved by consensus; if consensus is not achieved, a third blinded reviewer will adjudicate. Reliability estimates will be reported with confidence intervals as part of study quality assurance.

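### The mRUS reading that decides whether the 8- and 10-week films are taken has no stated reader or film set, and its criterion is looser than the primary endpoint's

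*Protocol*

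**What the plan says.** **Scheduling.** The next visit is fixed as an item of the 6-week visit (Protocol 6.2.8) and of the 8-week visit (6.2.9). At week 6: "If bone healing is sufficient (mRUS ≥ 11 in all fractured bones), the next visit will be scheduled at 3 months postoperatively". For insufficient healing the rule reads: "defined as an mRUS < 11 in any fractured bone, a follow-up visit will be scheduled at 8 weeks". For week 10, 6.2.10 says: "This visit is only performed if bone healing was not sufficient at Visit X (8 weeks), defined as mRUS < 11 in any fractured bone". The criterion is the mRUS sum alone. No reader and no film set are named.

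**Endpoint.** Section 7.1.1.3 requires a sum of at least 11, a score of 3 or more in at least three of the four cortices, and no cortex scored 1, in all fractured bones. Section 7.1.1.5 sets the reading: "All masked radiographs will be assessed independently by two blinded reviewers", with consensus and then a third reader for discrepancies. It adds: "Images will be presented in random order and without access to clinical data or treatment allocation". The only timing given is in the synopsis (Imaging review), which places these reads during the study.

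**Films and blinding.** Section 6.3.7.2 states: "Clinical care will continue to rely on unedited radiographs in the medical record". Section 7.1.1.4 contrasts the largely radiolucent BIN with the comparator, "whereas titanium nails are inherently radiopaque". Section 6.3.7.4 nevertheless lists follow-up clinicians among the blinded parties, and mentions edited images only for those reviewing radiographs.

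**Analysis.** Section 8.3.6 justifies the interval-censored Weibull model by radiographic assessment every 2 weeks.

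**The concern.** Two readings of the same film serve different purposes. One decides whether further films exist; the other decides when the child healed. If the first says healed and the second says not healed, the films that would have located the event were never taken, and no later analysis can recover them.

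The disagreement can arise in two ways. First, the criteria differ, so one careful reader applying both rules to one film can reach both answers. Second, the readers and films may differ. The text points to an on-site reading of unedited films, which show the implant. That would sit badly with the blinding listed in 6.3.7.4.

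At stake are precision around weeks 6 to 12 and, if over-calling differs by arm among children close to union, a shift in the estimated difference.

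**Working it through.** **1. The plan's own figure.** Inputs from 8.2: one-sided alpha 0.025, power 0.90, SD 3, margin 3, true difference 0. n = 2 × (1.960 + 1.282)² × (3/3)² = 21.01, so 22 per group; 22/0.90 = 24.4, so 25. Both reproduce and neither is in dispute.

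**2. Interval widths from the visit schedule.**
- All 2-week films taken to week 12: every interval is 2 weeks wide.
- Healed for scheduling at week 6, not healed on the masked read: films at 6 and 12 only, interval (6,12], 12 − 6 = 6 weeks.
- The same at week 8: (8,12], 4 weeks.
- The reverse disagreement (site says not healed, masked read says healed) only adds a film and leaves the interval unchanged.

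**3. Scheduling criterion against endpoint criterion.** There are 4⁴ = 256 cortex patterns. Those with a sum of at least 11:
- Meeting 7.1.1.3: 2-3-3-3 (4 orderings), 2-3-3-4 (12), 2-3-4-4 (12), 2-4-4-4 (4), all cortices 3 or 4 (16). Total 48.
- Failing it: 1-2-4-4 (12), 1-3-3-4 (12), 1-3-4-4 (12), 1-4-4-4 (4), 2-2-3-4 (12), 2-2-4-4 (6). Total 58.

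48 + 58 = 106. This counts patterns with equal weight; it is not a clinical frequency.

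**4. Where the conditional films fall.** Section 8.2.2 gives mean 8 and SD 3 weeks. Assuming a Weibull shape, these imply shape 2.897 and scale 8.972. The share unhealed at week 6 is exp(−(6/8.972)^2.897) = 73%; the share healing between weeks 6 and 12 is 63%. Most events fall in the window covered by the conditional films.

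**5. Effect on the estimate.** The documents give no over-call rate, so every rate here is an assumption. Interval-censored Weibull AFT, difference in medians, Wald interval, 30 per arm, 1,000 runs. An over-call is a child unhealed on the masked read but called healed for scheduling at week 6 or 8. *Unrelated* means any unhealed child may be over-called; *near union* means only children who heal within the next 2 weeks.

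| Over-calls | Bias, true delay 3 wk | False non-inferiority | Bias, no true delay | SE, no true delay |
|---|---|---|---|---|
| None | 0.00 | 4.7% | +0.04 | 0.74 |
| Unrelated, 25% both arms | −0.03 | 4.3% | −0.02 | 0.77 |
| Unrelated, 50% TEN only | +0.03 | 3.4% | −0.01 | 0.77 |
| Unrelated, 50% BIN only | −0.05 | 4.4% | +0.01 | 0.77 |
| Near union, 25% both arms | −0.09 | 5.5% | 0.00 | 0.77 |
| Near union, 25% TEN only | −0.18 | 5.5% | −0.14 | 0.76 |
| Near union, 50% TEN only | −0.40 | 8.9% | −0.29 | 0.76 |
| Near union, 25% BIN only | +0.06 | 2.7% | +0.13 | 0.76 |
| Near union, 50% BIN only | +0.12 | 2.0% | +0.30 | 0.76 |

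Monte Carlo error is about 0.03 weeks on the bias at a 3-week delay (1.0/√1000) and 0.5-0.9 points on the error rate. The 4.7% in the first row comes from the small-sample Wald interval, not from this issue.

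A second simulation (27 per arm, 600 runs, profile intervals) agrees in direction. Equal shares of 20-40% gave negligible bias and an SE 3-5% higher. With 40% in TEN against 10% in BIN the shift was −0.15 to −0.18 weeks, and error at the margin went from 2.7% to 3.7%. With 50% against 0% it was −0.25 weeks and 4.2%. Reversing these lowered power at no true difference from 93% to 89% and 88%.

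**The case against.** A reader might infer that an unblinded, arm-aware reading determines the primary endpoint. The documents do not support that. No section says the scheduling mRUS is read on unmasked films; this is inferred from 6.3.7.2 and 7.1.1.4, and 6.3.7.4 points the other way. Healed status for the endpoint still comes only from masked readers. The scheduling read can affect only which films exist, and it widens an interval only under one direction of disagreement.

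Nor is it right that the masked result could not be available in time. Weeks 6 and 8 are two weeks apart, the synopsis has reads during the study, and nothing makes the booking final at the visit. What is missing is a named reader and a turnaround.

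The size is modest. Without differential over-calling near union the loss is slight, and the direction of any shift is unknown. Several differences in error rate (2.7% to 3.7%, 4.7% to 5.5%) are within about one Monte Carlo standard error. A 6-week interval for one child is also not comparable with a 3-week margin on a group difference.

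The synopsis and 8.2 state the endpoint as mRUS of at least 11 without the cortex conditions. If that short form governed, the mismatch of criteria would vanish, but 7.1.1.3 is the section that sets the primary threshold.

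Finally, 8.3.10 lets missed radiographs widen the interval, and 6.2.17.2 leaves sensitivity analyses for informative missingness to the SAP. Those passages concern missed films, not films the schedule never asks for, and an analysis cannot restore a film that was not taken.

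What stands: the reader and films are unspecified, the two criteria differ in the text, and the 2-weekly assessment assumed in 8.3.6 is not assured after week 6.

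**Conclusion.** The point holds as a gap and an inconsistency in the protocol, and should be settled before enrolment (estimated May 2026). The mismatch between 6.2.8-6.2.9 and 7.1.1.3 needs no assumption about unblinding or misreading: following the rules as written can skip the 8- and 10-week films for a child who has not met the endpoint.

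The expected damage is limited. With equal over-calling it is mainly an SE about 3-5% higher. In the simulations, shifts of roughly 0.15 to 0.4 weeks required over-calls that were concentrated near union and differed by arm, at assumed rates of 25-50%. Over-calling in TEN favours a non-inferiority conclusion; over-calling in BIN costs power. All of this rests on a Weibull shape with the protocol's mean 8 and SD 3, and on over-call rates that the documents do not give. A demonstrated unblinding of the endpoint is not part of the conclusion.

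**What to change.** - In 6.2.8 and 6.2.9 replace the sum of at least 11 with the full 7.1.1.3 criterion in all fractured bones, and align the opening conditions of 6.2.9 and 6.2.10.
- State that the next 2-week film stays booked by default and is cancelled only when a masked read by the existing readers meets that criterion. If no masked read is back in time, the film is taken.
- Record any on-site mRUS separately and keep it out of the endpoint.
- Reword 8.3.6 so that 2-weekly assessment runs to week 12 or until the masked read meets 7.1.1.3.

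Cost: masking, two reads and any adjudication must be completed in under two weeks for the 6- and 8-week films. Rolling reads need batches mixed across children and time points, so that the random-order presentation of 7.1.1.5 survives. A few children will have an extra visit and film. The scheduled visits number 7 without and 9 with weeks 8 and 10, so each child stays within the 7-9 visits of 9.2. Each added examination is about 0.002 mSv on the figure in 9.3.1. The expected burden in both sections should be updated. The sample size does not change.
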